14.2.5 Time to ICU Admission (Day 1 Through Day 28)

Time to ICU admission will be based on data collected on the ‘Hospitalization’ eCRF page.

Time to ICU admission is defined as the time from first dose (Day 1) to the date/time of ICU admission, or death, whichever occurs first, in days:

- Time to ICU admission (days) = (Date/time of ICU admission – Date/time of first dose)

The rules below to define censoring/event dates will be followed:

| # | Description | Date of Event or Censoring | Outcome |
|---|---|----------------------------------|----------|
| 1 | Subject with first dose administered while in ICU | Date of first dose of study drug | Censored |

| | | | |
|---|---|---|----------|
| 2 | ICU admission or Death from Day 1 up to D28 | Earliest between date of ICU admission and date of death (in case of death) | Event |
| 3 | For subjects never admitted to ICU and not died | Earliest between D28 and date of discontinuation | Censored |

Number and percentage of subjects with and without the event will be summarized.

The hypotheses that will be tested for each dose level using a one-sided stratified log-rank test of time to ICU admission with use of corticosteroids at a prednisone equivalent daily dosage of ≤ 15 mg or > 15 mg within 48 hours prior to randomization, and country as stratification factors, are:

- H_{0i} : $HR_i \geq 1$
- H_{1i} : $HR_i < 1$

where

- HR_i denotes the Hazard Ratio of M5049 dose i versus placebo
- i denotes M5049 50 mg BID or M5049 100 mg BID
- $HR_i < 1$ denotes an improvement compared to placebo.

Estimation of effect each treatment dose (and 95% two-sided CI) separately compared to placebo will be based on hazard ratio from stratified Cox-model of event hazard rate, with terms for treatment arm (each active treatment separately against placebo), use of corticosteroids at a prednisone equivalent daily dosage of ≤ 15 mg or > 15 mg within 48 hours prior to randomization, and country. Ties will be handled using the discrete method.

Event-free survival function for time to event will be estimated via Kaplan-Meier (product-limit) method by treatment group and presented in a tabular and graphical format together with associated statistics (median time to event, event rates at Day 7, Day 14, Day 21 and Day 28) including the corresponding two-sided 95% CI. The estimates of the standard error (SE) will be computed using Greenwood's formula.

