5.1 Inclusion Criteria

Participants are eligible to be included in the study only if all the following criteria apply during the 48-hour study Screening Period:

Informed Consent

- Participant (or legally authorized representative) provides signed informed consent prior to the initiation of any study assessments for participation in the study.

Age

- Are ≥ 18 to ≤ 75 years of age, at the time of signing the informed consent.

Type of Participant and Disease Characteristics

- Has laboratory-confirmed SARS-CoV-2 infection as determined by nucleic acid amplification test, polymerase chain reaction, antigen test, or other commercial or public health assay (based on locally accepted guidelines) in a sample collected < 10 days prior to randomization.
- Documentation of chest imaging consistent with COVID-19 pneumonia (as per locally accepted guidelines). If chest imaging is not available during Screening, please discuss with

Medical Monitor or designee regarding evidence of probable COVID-19 pneumonia for study participant eligibility.

5. Not on mechanical ventilation (invasive or noninvasive), or ventilation, or ECMO, nor (based on medical judgement of admitting physician) anticipated to be in the next 24 hours.
6. An SpO₂ < 94% in room air AND able to maintain a PaO₂/FiO₂ ≥ 150 (or equivalent SpO₂/FiO₂ ≥ 190) with a maximum FiO₂ 0.4. These readings may be obtained after exertion by the participant. Note: if participant is on chronic low O₂ therapy (≤ 2 L), assess their current baseline O₂ requirements for eligibility.
7. Requiring hospitalization (i.e., in the process of hospital admission or already admitted).

Birth Control based on Sex at Birth

8. a. Female Participants:

- Not a woman of childbearing potential (See [Appendix 2](#)).

OR

- If a woman of childbearing potential:

- Is using a depot contraceptive or extended cycle oral contraceptive from before the first dose of the study intervention(s).
- Agree not to become pregnant or donate eggs (ova, oocytes) for reproduction for a full 60 days.
- Use a highly effective contraceptive method (i.e., with a failure rate of < 1% per year) as described in [Appendix 2](#) for the duration of the study (a full 60 days), either with:
 - A daily use hormonal contraception from before the first dose of the study intervention(s),

OR

- Uses a barrier method during the length of the study (a full 60 days).

b. Male Participants:

- Agree to refrain from donating sperm for at least 90 days.

PLUS, either

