Time to ICU admission (hereafter, “event”) is defined as the time from first dose (Day 1) to the date of event up to Day 28. Participants completing or withdrawing from the study without experiencing the event, will be censored at the time of completion or withdrawal. If death occurs before the event, it will be counted as an event.

Analysis will be based on a stratified log-rank test of distribution of time to event with strata defined by (1) the use of corticosteroids at a prednisone equivalent daily dose of ≤ 15 mg or > 15 mg within 48 hours prior to randomization, (2) the use of antiviral therapy including convalescent plasma (presence or absence) within 48 hours prior to randomization, and (3) country.

Estimation of treatment effect by dose (and 95% two-sided CI) compared to placebo will be based on hazard ratio from a stratified Cox-model of response hazard rate, with terms for treatment group and strata defined as above.

Event-free survival function for time to event will be estimated via the Kaplan-Meier method by treatment group and presented together with associated statistics (median time to event, response rates at Day 9, Day 14 and Day 28) including the corresponding two-sided 95% CI.

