14.2.8 Total Days in ICU

Total days in ICU will be based on data collected on the ‘Hospitalization’ eCRF page.

Total days in the ICU are defined as the sum, for all ICU admissions, of the time from ICU admission to the date of ICU discharge, in days:

$$\text{Total days in the ICU (days)} = \sum_h (\text{Date/Time of ICU discharge} - \text{Date/Time of ICU admission})$$

where h = number of ICU admissions during the study.

In case of ICU admission and discharge prior to first dose, the occurrence will not be considered for derivation of total days in ICU. In case ICU admission prior to and discharge after first dose, date and time of first dose will be used in place of date and time of ICU admission for calculation of total days in ICU.

The following information will be presented:

- Number and percentage of participants admitted in ICU
- Number and percentage of participants with more than one ICU admission
- Number and percentage of participants in the following discharge categories: death in ICU, discontinuation in ICU, discharged from ICU.
- Summary statistics of duration of ICU stay.

Participants never admitted to ICU will not be considered for descriptive statistics derivation.

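### Time to ICU admission or death: the rule censoring participants dosed while in ICU at time zero has no condition on death, so it conflicts with the endpoint's definition and event rule, and no precedence is stated

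*SAP*

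**What the plan says.** SAP 14.2.5 defines the endpoint as the time from first dose "to the date/time of ICU admission, or death, whichever occurs first". Its table then has three rows:

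- Row 1: "Subject with first dose administered while in ICU" is censored at the date of first dose.
- Row 2: "ICU admission or Death from Day 1 up to D28" is an event, at the earlier of the two dates.
- Row 3: "For subjects never admitted to ICU and not died" is censored at the earlier of Day 28 and discontinuation.

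The SAP does not say which row wins when two apply. The same section asks for counts of participants with and without the event.

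Protocol 10.4.3.5 has no counterpart to row 1. On death it says: "If death occurs before the event, it will be counted as an event". Participants who complete or withdraw without the event "will be censored at the time of completion or withdrawal". SAP Section 7, which lists changes from the protocol's analyses, covers only the stratification factors.

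SAP 14.2.6 and 14.2.7, for noninvasive and invasive ventilation, count death through Day 28 as an event and have no row that censors at first dose.

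**The concern.** Row 3 applies only to participants who have not died; row 1 carries no such limit. A participant in ICU at first dose who dies by Day 28 therefore meets row 1 (censored, time zero) and row 2 (event, date of death). Row 1 is listed first and is unconditional, so a programmer following the table downward would lose the death.

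The case can arise. Protocol inclusion criterion 5 requires participants to be "Not on mechanical ventilation (invasive or noninvasive), or ventilation, or ECMO", which bars ventilatory support but not an ICU bed. SAP 14.2.8 also plans for it: "In case ICU admission prior to and discharge after first dose", the date and time of first dose replaces the admission date and time.

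At stake is whether a measure of deterioration that includes death counts every death in the treated population, and whether its percentage table and its models describe the same people.

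**Working it through.** The documents give no event count or power for this endpoint, so there is no planned figure to reproduce. The check is to apply the rules to one participant and then size the effect under stated assumptions.

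**One participant: in ICU at first dose, dies on Day 10.**

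| Rule | Time | Status |
|---|---|---|
| SAP 14.2.5, row 1 | 0 | Censored |
| SAP 14.2.5, definition and row 2 | Day 10 | Event |
| SAP 14.2.6 and 14.2.7, if not ventilated before death | Day 10 | Event |

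Under row 1 the participant is in no risk set at any event time. The log-rank, Cox and Kaplan-Meier results are those of an analysis that leaves the participant out. In the count table the same participant stays in the denominator and falls on the side without an event.

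**Crude size.** Planned total 150 (protocol 4.1), randomized 1:1:1, gives 150 / 3 = 50 per arm. One death is 1 / 50 = 2 percentage points of the crude event rate.

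**Expected deaths affected across the trial** = 150 × share in ICU at first dose × Day 28 mortality among them. The documents give neither rate; all values below are assumptions.

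| Share in ICU | Mortality | Expected deaths |
|---|---|---|
| 2% | 10% | 150 × 0.02 × 0.10 = 0.3 |
| 5% | 20% | 150 × 0.05 × 0.20 = 1.5 |
| 10% | 20% | 150 × 0.10 × 0.20 = 3 |
| 10% | 40% | 150 × 0.10 × 0.40 = 6 |
| 20% | 40% | 150 × 0.20 × 0.40 = 12 |

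**Illustrative arm of 50 (invented).** Forty-five participants are not in ICU at first dose, and five of them have events on Day 5. Five are in ICU at first dose, and two of them die on Day 10. Everyone else is followed to Day 28.

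- Row 1 applied first: crude 5 / 50 = 10.0%; Kaplan-Meier at Day 28, 5 / 45 = 11.1%.
- Deaths counted: crude 7 / 50 = 14.0%; Kaplan-Meier 1 − (45/50) × (43/45) = 14.0%.

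Under row 1 the crude and Kaplan-Meier rates differ although nobody was lost to follow-up, because they rest on 50 and 45 people.

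**The case against.** A participant already in ICU cannot have a first ICU admission, so restricting the endpoint to those at risk of one is reasonable. Not counting the ongoing stay as an event is sound. The difficulty is confined to death.

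Row 2 is unconditional too, so the SAP could be read as counting the death. That is fair: strictly, the table gives two answers, and the loss of the death follows from reading it in order.

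The protocol's sentence speaks of death before ICU admission and does not plainly address someone admitted before dosing; the SAP may be filling a gap. The SAP's modification history also says that time-to-event censoring rules were updated. But that note does not identify this rule, and the protocol has no exception that would take these participants out.

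A reader might infer that the rule biases the comparison or could reverse the hazard ratio. The documents do not support this. ICU status at first dose is in effect a baseline characteristic, since allocation is blinded and made just before dosing (protocol 7.1), so selecting on it favors neither arm. No calculation shows a change of direction. A reader might also infer that the models treat these participants as event-free. They do not: the models leave them out, and only the count table shows them without an event.

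Eligibility (FiO2 at most 0.4, PaO2/FiO2 at least 150 or the SpO2/FiO2 equivalent, no ventilation present or anticipated within 24 hours) suggests that few participants may be affected.

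**Conclusion.** The point holds as a conflict between row 1 and the endpoint's own definition and event row, with no precedence stated and no declaration in Section 7. Followed in table order, it is an undeclared exclusion of treated participants from an analysis assigned to the ITT set (SAP Sections 8.1 and 14), and it tabulates people who died as having had no event.

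The effect on results is unknown and could be nil. It depends on how many participants are in ICU at first dose and how many of them die by Day 28, neither of which the documents give. The firm figure is 2 percentage points of the crude rate per affected death in an arm of about 50. The expected counts above are only as good as their assumed rates.

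Consequences are bounded. The endpoint is secondary, all tests are exploratory (SAP Section 9), and the deaths still appear in all-cause mortality (SAP 14.2.4) and in both ventilation endpoints. The inconsistency should still be settled before unblinding, because the plan as written does not yield a single answer for these participants.

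**What to change.** Amend row 1 of SAP 14.2.5. For participants in ICU at first dose:

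- the ongoing ICU stay is not an event;
- death through Day 28 is an event on the date of death;
- otherwise, censor at the earlier of Day 28 and discontinuation.

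State the order in which the rows apply, and declare the rule in Section 7.

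As a sensitivity analysis, restrict to participants not in ICU at first dose, removing the others from both numerator and denominator. Report the number removed and their deaths by arm.

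The cost is SAP wording, one derivation and one extra run, using ICU and death data already collected. There is a small downside: for participants in ICU at first dose the composite reduces to death, so the estimand is slightly mixed. The sensitivity analysis shows whether that matters.

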14.2.6 Time to Non-Invasive Mechanical Ventilation (Day 1 Through Day 28)

Time to non-invasive mechanical ventilation will be based on data collected on the ‘Ordinal Scale for Clinical Severity’ eCRF page.

Time to non-invasive mechanical ventilation is defined as the time from first dose (Day 1) to the date/time of clinical status ≥ 5 , in days:

- Time to non-invasive mechanical ventilation (days) = (Date/time of clinical status ≥ 5 – Date/time of first dose)

The rules below to define censoring/event dates will be followed:

| # | Description | Date of Event or Censoring | Outcome |
|---|--|---|----------|
| 1 | Clinical status ≥ 5 or Death from Day 1 up to D28 | Earliest between date of clinical status ≥ 5 and date of death (as applicable) | Event |
| 2 | For subjects which never started mechanical ventilation and not died | Earliest between D28 and date of discontinuation | Censored |

Analyses will be performed as specified in Section [14.2.5](#).

14.2.7 Time to Invasive Mechanical Ventilation

Time to invasive mechanical ventilation will be based on data collected on the ‘Ordinal Scale for Clinical Severity’ eCRF page.

Time to invasive mechanical ventilation is defined as the time from first dose (Day 1) to the date/time of clinical status ≥ 6 , in days:

- Time to invasive mechanical ventilation (days) = (Date/time of clinical status ≥ 6 – Date/time of first dose)

The rules below to define censoring/event dates will be followed:

| # | Description | Date of Event or Censoring | Outcome |
|---|---|--|----------|
| 1 | Clinical status ≥ 6 or Death from Day 1 up to D28 | Earliest between date of clinical status ≥ 6 and date of death (in case of death) | Event |
| 2 | For subjects which never invasive started mechanical ventilation and not died | Earliest between D28 and date of discontinuation | Censored |

Analyses will be performed as specified in Section 14.2.5.

14.2.8 Total Days in ICU

Total days in ICU will be based on data collected on the ‘Hospitalization’ eCRF page.

Total days in the ICU are defined as the sum, for all ICU admissions, of the time from ICU admission to the date of ICU discharge, in days:

$$\text{Total days in the ICU (days)} = \sum_h (\text{Date/Time of ICU discharge} - \text{Date/Time of ICU admission})$$

where h = number of ICU admissions during the study.

In case of ICU admission and discharge prior to first dose, the occurrence will not be considered for derivation of total days in ICU. In case ICU admission prior to and discharge after first dose, date and time of first dose will be used in place of date and time of ICU admission for calculation of total days in ICU.

The following information will be presented:

- Number and percentage of participants admitted in ICU
- Number and percentage of participants with more than one ICU admission
- Number and percentage of participants in the following discharge categories: death in ICU, discontinuation in ICU, discharged from ICU.
- Summary statistics of duration of ICU stay.

Participants never admitted to ICU will not be considered for descriptive statistics derivation.

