10.4.3.2 Analysis of Clinical Status

The number and percentage of participants in each clinical status category will be presented by treatment group and by time point in a graphical manner.

An ordinal logistic regression model will be used to compare the clinical status from Day 1 through Day 60 of M5049 groups to placebo. Under the assumption of proportional odds, a summary odds ratio and its 95% CI will be estimated for each M5049 group versus placebo. A test for the proportionality assumption will also be made.

Separate odds ratios will also be estimated for dichotomized version of the health status:

- Death versus any other category.
- Worsening versus stable/improvement.
- Not discharge versus hospital discharged.

An exploratory longitudinal analysis will be run to account for all of the time points and present estimates of treatment effect by time point.

10.4.3.3 Analysis of Time to SpO₂ of $\geq 94\%$ Sustained for at Least 24 hours in Room Air

The time to response is defined as the time from first dose (Day 1) to the date of the first SpO₂ $\geq 94\%$ sustained for at least 24 hours in room air up to Day 28. For participants who die and those considered as failure (that includes use of mechanical ventilation, ICU admission leading to treatment discontinuation, and relapse) the time to response will be censored at Day 28. For participants completing the study without meeting response or failure, the time to response will be censored at Day 28. Participants withdrawn before the End of Study Visit without meeting response or failure will be censored at the last date of SpO₂ assessment in room air temperature.

Cumulative distribution function for time to response will be estimated via the Kaplan-Meier (product-limit estimates) method by treatment group and presented together with associated statistics (median time to response, response rates at Day 7, Day 14, and Day 28) including the corresponding two-sided 95% CI.

10.4.3.4 Analysis of All-cause Mortality Through Day 60

Number and percentage of death through Day 60 with 95% CI will be presented by treatment group.

10.4.3.5 Analysis of Time to Intensive Care Unit Admission (Day 1 Through Day 28)

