10.4.3.8 Analysis of Total Days in ICU

The total number of days in ICU from Day 1 through Day 60 will be described together with 95% CI by treatment group.

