10.4.3.9 Analysis of Total Days in the Hospital and Time to Hospital Discharge

The total number of days in the hospital from Day 1 through Day 60 will be described together with 95% CI by treatment group.

In addition, time to hospital discharge will be analyzed. The time to hospital discharge is defined as the time from first dose (Day 1) through Day 28 to hospital discharge. For participants who die and those considered as failure (that includes use of mechanical ventilation, ICU admission leading to treatment discontinuation, and relapse), the time to hospital discharge will be censored at Day 28. For participants completing the study without being discharged or failure, the time to hospital discharge will be censored at Day 28. Participants withdrawn before the End of Study Visit without hospital discharge or failure will be censored at the last date of available clinical status assessment.

[figure not shown]
Cumulative distribution function for time to hospital discharge will be estimated via the Kaplan-Meier (product-limit estimates) method by treatment group and presented together with associated statistics (median time to hospital discharge, hospital discharge rates at Day 7, Day 14, and Day 28) including the corresponding two-sided 95% CI.

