14.2.4 All-cause Mortality

All-cause mortality analysis will be based on data collected on the ‘Death’ eCRF page.

All-cause mortality is defined as the proportion of subjects who died during the study, regardless of the cause of death.

Number and proportion of subjects dying through Day 60 and the corresponding two-sided Wilson 95% CI will be provided by treatment groups based on the ITT analysis set.

In case more than 6 deaths are observed, the difference in proportion of each dose to placebo will be presented with two-sided 95% CIs based on the Miettinen-Nurminen method. In addition, summary score estimates of the common difference in proportion, stratified for use of corticosteroids at a prednisone equivalent daily dosage of ≤ 15 mg or > 15 mg within 48 hours prior to randomization, AVT use in the 48h prior to randomization and country will be presented with 95% CIs based on stratified Newcombe confidence limits.

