14.2.9 Total Days in the Hospital and Time to Hospital Discharge

Total days in the hospital will be based on data collected on the ‘Hospitalization’ eCRF page.

Total days in the hospital are defined as the sum, for all hospitalization events, of the time from first dose to the date of hospital discharge, in days:

- Total days in the hospital (days) =
 First hospitalization: *Date of hospital discharge – Day 1 + 1*
 +
 Subsequent hospitalization: *Date of discharge – date of admission + 1*

In other words, in case of hospital admission prior to and discharge after first dose, date of first dose will be used in place of date of hospital admission for calculation of total days in the hospital. In case of multiple hospitalizations, the total number of days of each event will be added up.

The following information will be presented:

- Number and percentage of participants with more than one hospital admission (only non-consecutive hospitalization will be included in the count)
- Number and percentage of participants in the following discharge categories: death in hospital, discontinuation in hospital, discharged from hospital.
- Summary statistics of duration of hospital stay.

In addition, time to hospital discharge will be based on data collected on the ‘Hospitalization’ eCRF page from Day 1 through Day 28.

The time to hospital discharge, defined as the time from first dose (Day 1) to the date of first hospitalization discharge, in days:

- Time to hospital discharge (days) = (Date of first hospitalization discharge – Date of first dose)

The rules for the different types of censoring/event below will be followed:

| # | Description | Date of Event or Censoring | Outcome |
|---|-------------|----------------------------|---------|
|---|-------------|----------------------------|---------|

| | | | |
|---|---|--|----------|
| 1 | Death from Day 1 up to D60/Study completion | D28 | Censored |
| 2 | Failure at any point and time during the study from D1 up to D28, defined as: * ICU admission leading to treatment discontinuation * use of mechanical ventilation * relapse | D28 | Censored |
| 3 | Hospital discharge before Day 28 | Date of hospital discharge | Event |
| 4 | No hospital discharge before Day 28/discontinuation without death or failure | Earliest between D28 and date of discontinuation | Censored |

Analyses will be performed as specified in Section 14.2.3.

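### SAP 14.2.8 summarises ICU days only among participants admitted to ICU, and 14.2.8 and 14.2.9 omit the protocol's by-group 95% CI without declaring it

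*SAP*

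**What the plan says.** Protocol 3.2 and SAP 5.2 give the same secondary objective: length of ICU stay, M5049 compared with placebo, measured as total ICU days from Day 1 through Day 60.

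Protocol 10.4.3.8 plans: "The total number of days in ICU from Day 1 through Day 60 will be described together with 95% CI by treatment group". Protocol 10.4.3.9 plans the same for hospital days: "The total number of days in the hospital from Day 1 through Day 60 will be described together with 95% CI by treatment group". Neither sentence names a denominator.

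SAP section 14 bases efficacy analyses on the ITT set (all treated participants) unless stated otherwise. Section 14.2.8 lists "Number and percentage of participants admitted in ICU", then the number with more than one admission, the discharge categories (including death in ICU) and summary statistics of duration. It ends: "Participants never admitted to ICU will not be considered for descriptive statistics derivation". For total hospital days, section 14.2.9 lists "Summary statistics of duration of hospital stay". Neither section names a CI for total days.

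The default statistics for continuous variables in SAP 9.1 are n, mean, SD, median, quartiles, minimum and maximum. SAP section 9 fixes the level and sidedness of CIs but does not attach one to every summary. SAP section 7 declares one change to the protocol's analyses, which concerns stratification factors.

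**The concern.** ICU admission is itself an outcome that M5049 may change. SAP 14.2.5 analyses time to ICU admission or death as a measure of deterioration, by dose against placebo. Averaging ICU days only among those admitted conditions on that outcome, so the row no longer compares the full treatment groups. A drug that prevents mainly short stays leaves the long ones behind and raises the admitted-only mean even though total ICU use falls. The selection is largely, not wholly, after randomisation: SAP 14.2.5 has a rule for "Subject with first dose administered while in ICU", and 14.2.8 provides for admission before first dose.

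The study tests no confirmatory hypothesis, so no formal decision is at stake. What is at stake is whether a descriptive secondary row can be read as the comparison its objective announces, and whether two summaries keep the precision the protocol specified.

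**Working it through.** **1. The CI: protocol and SAP side by side.** These are the secondary summaries that are not time-to-event and for which the protocol asks for a by-group 95% CI.

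| Summary | Protocol | SAP | CI in SAP? |
|---|---|---|---|
| Mortality to Day 60 | 10.4.3.4 | 14.2.4 | Yes, Wilson |
| Total ICU days | 10.4.3.8 | 14.2.8 | No |
| Total hospital days | 10.4.3.9 | 14.2.9 | No |
| Relapse | 10.4.3.12 | 14.2.12 | Yes, Wilson |
| Re-hospitalisation | 10.4.3.13 | 14.2.13 | Yes, Wilson |

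For mortality, the protocol's "Number and percentage of death through Day 60 with 95% CI will be presented by treatment group" becomes "Number and proportion of subjects dying through Day 60 and the corresponding two-sided Wilson 95% CI will be provided by treatment groups" in the SAP. The two length-of-stay summaries have no such counterpart. Sections 9 and 9.1 do not supply the CI, and section 7 does not mention its removal.

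The Kaplan-Meier summaries are outside this list and keep their CIs. Time to hospital discharge keeps its CI because 14.2.9 refers to 14.2.3.

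**2. The denominator: illustration.** The documents give no admission rate or length of stay for this endpoint, so there is no plan figure to reproduce. From the protocol: 150 participants, 1:1:1, hence 150/3 = 50 per arm. Assumed: on placebo 12 are admitted, six for 4 days and six for 14 days.

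Placebo:
- Admitted only: (6×4 + 6×14)/12 = 108/12 = 9.0 days.
- All treated: 108/50 = 2.16 days.
- Sum of squares 6×16 + 6×196 = 1272; SD over 50 = √[(1272 − 50×2.16²)/49] = 4.60.

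Example A, active prevents the six short stays:
- Admitted only: 84/6 = 14.0, against 9.0. Active looks worse.
- All treated: 84/50 = 1.68, against 2.16. Active has fewer ICU days. SD 4.60.
- Difference 1.68 − 2.16 = −0.48; SE = √[(4.60² + 4.60²)/50] = 0.92; 95% CI −0.48 ± 1.96×0.92 = −2.28 to 1.32. This interval would not establish direction either.

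Example B, active prevents three of each:
- Admitted only: 54/6 = 9.0, against 9.0. No difference shows.
- All treated: 54/50 = 1.08, against 2.16. Use is halved; difference −1.08, 95% CI −2.67 to 0.51.

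In general, if a short and b long stays are prevented, the admitted-only mean minus 9 equals 5(a − b)/(12 − a − b). It points the wrong way whenever a > b, shows nothing when a = b, and points the right way when a < b. Leaving out none prevented and all prevented, that is 21, 5 and 21 of 47 combinations. The symmetry comes from the assumed set-up, so these are not probabilities.

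Varying the inputs: with 10%, 20% or 30% admitted on placebo, stays of 4 or 12 days split about evenly, and half or all of the short stays prevented, admitted-only means are 8.0 to 8.8 (placebo) and 9.0 to 12.0 (active). All-treated means are 0.88 to 2.48 and 0.72 to 2.16. All six cases reverse, because only short stays are ever prevented.

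**3. The all-treated mean needs a companion.** Suppose active has the same 12 admissions, but three of the 14-day stays end in death after 2 ICU days.
- Mean ICU days: (6×4 + 3×14 + 3×2)/50 = 72/50 = 1.44, against 2.16. Active looks better.
- Mean days alive and out of ICU through Day 60: placebo, with no deaths assumed, 60 − 2.16 = 57.84. Active (38×60 + 6×56 + 3×46 + 3k)/50, where k is days out of ICU before those three admissions: 55.08 at k = 0 and 55.62 at k = 9. Active is worse.

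**The case against.** Length of stay in the ICU can reasonably be read as duration among those who stayed, and the protocol sets no denominator. The table in 14.2.8 gives the percentage admitted before the duration, so the all-treated mean can be recovered by hand: 12×9.0/50 = 2.16. SAP 14.2.5 compares time to ICU admission or death on the ITT set with hazard ratios and 95% CIs, so a halving of admissions would show there, and mortality is reported separately. The examples rest on invented stays, and the all-treated mean misleads too when patients die early.

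Much of this stands. It limits the point to a summary that can mislead if read alone. It does not remove it. Time to ICU admission or death stops at Day 28 and carries no information on duration. The all-treated mean can be recovered but is not presented, and the all-treated CI takes further hand calculation from the SD.

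On the CI, SAP 6.3 refers to all planned analyses identified in the protocol and in the SAP, which might be taken to keep the CI alive. That sentence mainly sets the timing of the final analysis. It does not put a CI into 14.2.8 or 14.2.9.

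A reader might infer that the restriction to admitted participants breaches the protocol, or that the SAP hides ICU use. The documents support neither: Protocol 10.4.3.8 is silent on the denominator, and the SAP reports admissions in two places. Nor has the hospital-stay objective lost all its precision, since time to discharge keeps its CI.

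**Conclusion.** Both parts hold, at modest weight. The admitted-only duration is a poor choice for a comparative objective, because the subset forms largely after randomisation and treatment can alter it. The harm is a potentially misleading exploratory secondary summary, partly offset by the percentage admitted, the ITT analysis of time to ICU admission or death, and mortality. The reversal (9.0 against 14.0 among admitted; 2.16 against 1.68 over all) and the masking (9.0 against 9.0; 2.16 against 1.08) show what can happen under assumed inputs, not what will.

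The missing by-group 95% CI for total ICU days and total hospital days is an undeclared departure from Protocol 10.4.3.8 and 10.4.3.9, and it needs no assumption. The protocol does not say which statistic the CI is for; the mean is assumed here.

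**What to change.** In SAP 14.2.8, add total ICU days from Day 1 through Day 60 over all ITT participants, counting those never admitted as 0. Give a by-group 95% CI for the mean and, as exploratory, each dose minus placebo with a 95% CI. Keep the admitted-only row, labelled descriptive.

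Because early death shortens ICU days, show the new row beside deaths by group, or beside days alive and out of ICU through Day 60. State how participants who withdraw before Day 60 are counted.

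In 14.2.9, restore the by-group 95% CI for total hospital days. List all these changes in section 7.

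The cost is SAP wording and a few table rows, using the Hospitalization and Death eCRF pages that the SAP already names; no new data are needed. The downside is a skewed, zero-heavy variable with a wide interval: in Example A, −0.48 days with a CI of −2.28 to 1.32, and an all-treated median of 0 in both arms.
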